## **5. Background and rationale**

Alcohol misuse is a global problem and is the third leading cause of disability in Europe (1). In the UK, there has been a consistent, year on year increase in harm related to alcohol. Alcohol-

related NHS hospital admissions have more than doubled since 2002/03, with an estimated 1,220,300 admissions related to alcohol in 2011/12 (2). Chronic health conditions related to alcohol have increased in prevalence in the UK, including liver cancer, pancreatitis, alcoholic liver-disease and alcohol use disorders (3). Mental health may be negatively affected by the chronic, heavy use of alcohol with increased risk of depression, anxiety, suicidality, psychosis and impairments to memory and other cognitive functions. Alcohol may contribute to social problems such as unemployment, criminality, marital breakdown, and domestic violence (4-7). The physical, mental and social problems associated with alcohol place a considerable burden on the UK economy. The estimated cost to the UK economy is £21 billion annually [18], of which the NHS costs are estimated at £3.5 billion (8).

The prevalence of alcohol dependence in the UK is estimated at 9.3% of men and 3.6% of women (9). The number of people entering specialist alcohol treatment has increased each year between 2008, when the Department of Health began collecting data, and 2012 (10). The number successfully completing treatment has also risen over the same reporting period but the majority of those dependent on alcohol undergo frequent episodes of withdrawal and resumption of drinking, as many as 70% of service users relapse in the first 12 months post treatment (11, 12). Improved treatment for alcohol dependence has been identified as a priority in the UK Government's Alcohol Strategy (8). Providing effective treatment for alcohol dependence to reduce relapse rates and therefore alcohol associated harms will contribute to this objective.

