## **6. Aims and objectives**

Aim:

1. To evaluate the acceptability, effectiveness and cost-effectiveness of adjunctive MM with and without CM in improving adherence to acamprosate for relapse prevention in alcohol dependence.

Objectives:

- I. To conduct an internal pilot study to assess the feasibility, recruitment and acceptability of the proposed MM and CM interventions for pharmacists and service users.
- II. To conduct a definitive three-arm, randomised controlled trial of the effectiveness of MM with and without CM compared to SS alone in enhancing adherence to acamprosate in alcohol dependence relapse prevention.
- III. To estimate the cost effectiveness of MM with and without CM compared to SS alone in enhancing adherence to acamprosate in alcohol dependence relapse prevention.
- IV. To assess the impact of adherence to acamprosate for alcohol dependence relapse prevention on abstinence and reduced alcohol consumption.

Primary effectiveness and cost-effectiveness hypotheses:

- MM and MM+CM will be more effective than SS alone in terms of the percentage of prescribed acamprosate taken, measured using the medication events monitoring system, supplemented by pill count and self-report at 6 months post-randomisation.
- MM and MM+CM will be more cost-effective than SS alone at 12 months post-randomisation.

Secondary hypotheses:

- MM and MM+CM will be more effective than SS in terms of the percentage of prescribed medication taken, measured using the medication events monitoring system, supplemented by pill count and self-report, at 12 months post-randomisation.
- Greater adherence to acamprosate will be associated with improved alcohol outcomes, namely a higher percentage of days abstinent, less units of alcohol per drinking day, longer time (latency) to first alcoholic drink, reduced relapse to any drinking and reduced relapse to heavy drinking at 6 and 12 months post-randomisation.
- Service user beliefs about medication, and therapeutic relationship with care providers, will moderate medication adherence at 6, and 12 months post-randomisation.

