#### *7.1.10.2 Secondary outcome measures*

At baseline assessment participant demographics will be collected as well as a history of use of acamprosate, other relapse prevention medication use, and previous medically assisted

detoxification using a medical history checklist devised specifically for the trial. The substance use section of the Alcohol, Smoking and Substance Involvement Screening Test- Lite (ASSIST-Lite;(13)) will be administered to obtain a history of any substance use.

Severity of dependence will be measured at the initial screening assessment and at 6 and 12 month follow-up using the Severity of Alcohol Dependence Questionnaire (SADQ) (85). The SADQ is a 20-item self-complete questionnaire containing items representing five domains of the alcohol dependence syndrome: (i) physical withdrawal signs (ii) psychological withdrawal signs (iii) withdrawal relief drinking (iv) tolerance (v) reinstatement following a period of abstinence.

Alcohol consumption will be measured using the Time Line Follow Back (TLFB) Form 90 (86), administered at initial screening assessment and at 6 and 12 month follow-up after initiation of acamprosate. Percentage days abstinent, units of alcohol per drinking day (1 UK unit = 8g alcohol), time to first alcoholic drink, relapse to any drinking and relapse to heavy drinking (8+/6+ units for males/females on a single occasion) will be computed.

Participants' beliefs about medications will be assessed using the Beliefs about Medications Questionnaire (BMQ; (87)). The BMQ assesses an individual's beliefs about medication specific to them and their health, as well as their general beliefs about medication. This questionnaire will be administered at initial screening assessment and at 6 month follow-up. The measure will be used to evaluate the impact of MM on beliefs and concerns about medication and the association with adherence to acamprosate.

Participants will be asked to rate their therapeutic relationship with the care provider monitoring their medication adherence at each follow up point using the STAR rating scale (88). Therapeutic relationship (or alliance) has been found to predict clinical outcome across a range of mental disorders (89) including alcohol dependence (90). This will be used as an additional process measure to assess the impact of therapeutic relationship on medication adherence and clinical outcome.

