### 7.2.4 Data analysis

In the main trial the primary outcome measure is percent prescribed medication taken at 24 weeks post-randomisation assessed using a triangulation method. After checking for distributional assumptions and employing necessary transformations, an initial multiple analysis of covariance will be undertaken using a mixed model approach addressing the observed differences between SS versus SS+MM versus SS+MM+CM. If this analysis provides evidence of effect a second analysis of covariance will explore the differences of SS versus SS+MM and SS versus SS+MM+CM. Covariates included in the analysis will include stratification variables, gender and body weight (<60kg or 60+ kg). Mean differences between the groups will be presented with associated 95% confidence intervals. Multiple imputation will be employed to address the nature of missing data and sensitivity analysis will address the influence of missing data on the observed outcome. Secondary analysis will address drinking outcomes at 6 and 12 months using appropriate modelling approaches and these will be adjusted for known confounders; SADQ, site, age and gender. Time to relapse and relapse to heavy drinking will be assessed using survival analysis. Further secondary analyses will explore adherence data at 12 months. We will explore the association between adherence and drinking outcomes using a linear regression adjusted for known confounders and include an adherence\*allocation interaction term. As with most trials the analysis plan will be refined throughout the course of the study and the final analysis plan prepared and agreed by the research team and Trial Steering Committee.

Further analysis will be conducted to identify interactions between variables, including ratings of therapeutic relationship, and fidelity of MM and CM delivery, on clinical and adherence outcomes. The analysis will be governed by an explicit data analysis plan agreed in advance by the Trial Steering Committee.

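### Linear regression is the only method named for relating adherence to drinking outcomes, yet three of the five hypothesised outcomes are censored times; the planned survival analysis should be extended to them

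*Protocol*

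**What the plan says.** Section 6 sets the secondary hypothesis: "Greater adherence to acamprosate will be associated with improved alcohol outcomes". It names five outcomes. Two are continuous (percentage of days abstinent and units per drinking day). The other three are "longer time (latency) to first alcoholic drink, reduced relapse to any drinking and reduced relapse to heavy drinking at 6 and 12 months post-randomisation". Objective IV, one of the trial's four objectives, rests on the same association.

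Table 1 (section 7.1.10) lists those three under the TLFB, each as a time. Section 7.1.10.2 adds that "time to first alcoholic drink, relapse to any drinking and relapse to heavy drinking (8+/6+ units for males/females on a single occasion) will be computed". The TLFB is scheduled at baseline, 6 months and 12 months only.

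Section 7.2.4 has three relevant sentences, in this order:

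- "Secondary analysis will address drinking outcomes at 6 and 12 months using appropriate modelling approaches", with adjustment for SADQ, site, age and gender.
- "Time to relapse and relapse to heavy drinking will be assessed using survival analysis".
- After a sentence on 12-month adherence: "We will explore the association between adherence and drinking outcomes using a linear regression adjusted for known confounders", with an adherence-by-allocation interaction.

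**The concern.** The third of those sentences gives one method for all drinking outcomes and makes no exception. Read with section 6, it applies ordinary linear regression to three event times. Such a model has no way to represent a participant known only to have been drink-free up to some date. The analyst must then choose a value for that person or leave the person out, and the protocol does not say which. The answer to a stated hypothesis can turn on that choice.

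Two errors are possible. If only participants who drank are analysed, the best outcomes leave the data and a real association shrinks. If the recorded time also reflects how long a participant was followed, and follow-up length goes with adherence, an association can appear where none exists. Section 7.1.10.1 makes that second link plausible: when all three adherence measures are missing for a month, the participant is scored as non-adherent. Loss therefore lowers measured adherence by rule.

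**Working it through.** **1. The plan's own figure.** With effect size 0.3, 80% power, two-sided alpha 0.05 and 2:1:1 allocation, the SS group needs (1.96 + 0.842)² × (1 + 2) / 0.3² = 7.85 × 3 / 0.09 ≈ 262. Each intervention arm needs 131, so the total is 262 + 131 + 131 = 524. Allowing for 30% attrition, 524 / 0.70 = 748.6, against 748 stated. The figures reproduce. The point does not depend on them beyond using 748 as the number randomised.

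**2. How much censoring to expect.** Section 5 gives "as many as 70% of service users relapse in the first 12 months post treatment". This is an upper figure for relapse, and the protocol gives no rate for a first drink. I take 50% to 70% with the event by 12 months. I assume constant hazards and 30% loss spread over 12 months, which is milder than the protocol's 30% at 6 months.

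- At 70%: event hazard −ln(0.3) = 1.204 per year and loss hazard −ln(0.7) = 0.357. Observed events = 1.204/1.561 × (1 − 0.3 × 0.7) = 0.771 × 0.79 = 61%, so about 39% are censored.
- At 50%: event hazard 0.693. Observed events = 0.693/1.050 × (1 − 0.5 × 0.7) = 0.660 × 0.65 = 43%, so about 57% are censored.

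**3. What linear regression does with such data.** Simulation: 748 participants, 400 runs per scenario, follow-up ending at 365 days. Assumptions not in the protocol: adherence Beta(0.8, 0.8) and fixed at time zero; log hazard ratio 0 or −0.5 from 0% to 100% adherence; loss either unrelated to adherence or with log hazard ratio −1.5 (e^1.5 ≈ 4.5 times higher at 0% than at 100%). Ranges span 50-70% with the event.

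Three codings are compared with a Cox model: (A) drinkers only; (B) censoring times entered as event times; (C) lost participants dropped and never-drinkers set to day 365.

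| Scenario | A | B | C | Cox |
|---|---|---|---|---|
| Real association, loss unrelated: power | 7-17% | 57-77% | 69-84% | 80-92% |
| Same: slope in days (truth 41-52) | 10-17 | 33-42 | 43-50 | – |
| No association, loss unrelated: rejection at 5% | 4-6% | 4-6% | 4-6% | 5% |
| No association, loss related: rejection at 5% | 16-17% | 68-93% | about 30% | 4-5% |

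Coding A keeps 9.8/40.7 = 24% to 16.9/51.6 = 33% of the true slope.

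**4. A variant closer to the TLFB schedule.** Suppose drinking is known only from the 6- and 12-month visits, 30% are lost by month 6 and those participants are left out. Drinkers-only regression then has 6-13% power, against 47-73% for Cox. The lost association therefore does not depend on continuous loss dates.

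**The case against.** The strongest reply is that section 7.2.4 already assigns survival analysis to relapse without limiting it to comparisons between arms. On that reading, event times get survival methods and only continuous outcomes get linear regression. This is possible but not stated. The survival sentence follows the analysis of drinking outcomes and does not name time to first drink. The adherence association then comes separately, with its own method and interaction term. At best the sentences need reconciling.

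A second reply is that the analysis is exploratory and the plan is to be refined and agreed before analysis. That makes the correction easy. It does not make the named method suit these outcomes.

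Other objections stand and limit the size:

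- A reader might infer that linear regression forces a choice between treating last contact as the drink date and dropping non-drinkers. Coding C is a third route, and when loss is unrelated to adherence its slope is nearly right.
- A reader might infer that a false association is likely in most analyses, from the 68-93% in the table. The protocol does not support this. The loss gradient is assumed. With a TLFB only at baseline, 6 and 12 months, someone lost before month 6 has no later drinking record to enter, and the protocol plans multiple imputation for missing data. Nowhere does it propose entering a contact date as a drink date.
- Cox looks well behaved here because the simulation fixes adherence at time zero. In the trial, adherence builds up over 24 weeks while first drinks occur. An ordinary Cox model with 24-week adherence as a baseline covariate would let later adherence predict earlier drinking.

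**Conclusion.** The point holds in this form: the only method named for the adherence association does not suit three of the five hypothesised outcomes, and the protocol does not say that the planned survival analysis covers them. The loss of a real association under drinkers-only regression is the firmer result (power about 7-17% against 80-92%, at the assumed log hazard ratio of 0.5 with unrelated loss). A false association is conditional on loss being related to adherence, which the missing-data scoring rule makes plausible but the protocol does not quantify. If loss is unrelated and never-drinkers are set to the end of follow-up, the bias is small, so censoring alone does not establish a false result. Linear regression remains reasonable for percent days abstinent and units per drinking day. The primary outcome and the randomised comparisons are not affected.

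**What to change.** In section 7.2.4, state that the survival analysis already planned also applies to the association of adherence with time to first drink, relapse to any drinking and relapse to heavy drinking. Specify two details:

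- Censor at the last date covered by a TLFB, not at a later contact where drinking was not recorded.
- Enter adherence as a time-varying covariate (monthly), or use adherence up to a landmark and analyse events after it among those still event-free, so that later adherence cannot predict earlier drinking.

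Limit linear regression to percent days abstinent and units per drinking day.

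The cost is a short amendment and slightly more analysis work on data already collected. A landmark analysis also gives up events before the landmark. Neither option removes confounding between adherence and drinking, so the result remains an association.

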### 7.2.5 Economic analysis

The economic evaluation will compare the costs and effects of SS+MM+CM and SS+MM compared to SS alone for adherence to acamprosate prescribed for alcohol dependence. The primary analysis will compare costs and cost effectiveness at 12 month follow up of (a) SS compared to SS+MM, and (b) SS compared to SS+MM+CM, in line with primary aims of the study. Secondary analyses will explore SS compared to SS+MM compared to SS+MM+CM in a three-way comparison. The primary economic perspective will be the health and social care provider (NHS/PSS). Broader patient and societal perspectives will be considered in sensitivity analysis (i.e. criminal justice contacts and criminal activity, patient travel costs). A cost-utility analysis will be conducted using quality-adjusted life-years (QALYs) based on the EQ-5D-5L, a more sensitive version of the EQ-5D, that is a measure of health-related quality of life extensively used in previous alcohol studies in the UK (e.g. UKATT Research Team (93)). QALYs will be calculated by estimating the area under the curve between each consecutive follow up point. Patient-level resource use will be collected using the Adult Service Use Schedule (ADSUS) modified for alcohol misuse (94) and treatment adherence from clinical records. The ADSUS includes items on the cost of crime. Resource use will be valued

using national tariffs (PSSRU, NHS National Reference Costs). Costs and QALYs will not be discounted as the trial time horizon is 12 months. Costs and QALYs will be adjusted for pre-specified baseline covariates (age, gender, alcohol dependence severity) including costs and utility values using generalised linear modelling methods. Missing cost and QALY data will be imputed using multiple imputation methods. Cost-effectiveness will be assessed by estimating incremental cost-effectiveness ratios (ICERs) (95). Interventions with ICERs below £20,000 per additional QALY are generally considered cost-effective by NICE. Decision uncertainty around cost and effectiveness estimates will be represented by cost-effectiveness acceptability curves (CEACs) generated using non-parametric bootstrap methods to account for non-normal joint distributions of costs and outcomes (96).

The costs and benefits of interventions for alcohol problems, such as alcohol-related complications and mortality, extend well beyond the usual time horizons of clinical trials. Lifetime costs and effects will be modelled using data observed in this trial (costs, QALYs, drinking outcomes) with appropriate observational data from long term cohorts (mortality, relapse rates) guided by published economic modelling methods (97, 98). Costs and QALYs in the model will be discounted as per NICE guidance at 3.5% per annum after the first year to reflect time preferences. We will conduct a systematic and critical review of the current literature reporting on modelling methods used in the context of cost-effectiveness analysis in alcohol interventions. The review will inform the structure and development of a model to estimate the long term cost-effectiveness of Medication Management (MM) and MM + Contingency Management (CM) compared to Standard Support and inform on data required to populate such a model. These data will include relapse rates; mortality and morbidity by drinking status, sex and age; treatment and disease costs; and health state utility values by drinking status. We will validate the model by running the trial data using other published models and comparing the results. The two models most likely to be relevant (the Sheffield Alcohol Policy Model and the York Drinking Patterns Model) both utilise Markov state transition models using drinking status (moderate, hazardous, harmful defined by alcohol consumption) compatible with our trial outcomes. The final model will apply the treatment effect observed at 12 months together with an appropriate relapse rate, to drinking status and associated mortality and morbidity rates, costs and QALYs. The primary outcome will be costs and QALYs over patients' lifetimes starting from the distribution of patients by drinking status, age and gender at 12 month follow up. Uncertainty in model inputs will be incorporated through probabilistic sensitivity analysis (PSA) where all inputs are randomly varied using probability distributions rather than mean values. One-way and multi-way sensitivity analyses will be used to explore structural and parameter uncertainty such as the impact of varying discount rates for QALYs and costs, and worst best case scenarios for long term compliance, relapse rates, treatment effect, treatment costs and potential subgroup analyses.

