#### *7.1.1.3 Treatment arm 3: Standard support plus medication management with contingency management (SS+MM+CM)*

Although available evidence suggests that MM enhances adherence to prescribed medication for relapse prevention in alcohol dependence, there is concern that attendance at MM sessions may be sub-optimal (77). To optimise attendance, participants will follow the same care pathway as those in the SS+MM arm of the trial but with the addition of CM. Incentives in the form of vouchers (not redeemable for alcohol) will be provided to reinforce attendance at MM sessions by telephone with the pharmacist. The CM procedure and value of the incentives has been informed by the available literature on CM in substance misusers (69) and alcohol dependence (13) and focus groups with service users with experience with treatment services for alcohol dependence. Participants will receive between £2 and £10 in the form of a voucher for each MM session completed, with a total value of up to £120 for completing all support sessions. After each MM session a SMS text message will be sent to the participant to inform them that they have been awarded a voucher, the magnitude of the voucher and the total voucher value received to date.

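### The primary cost-effectiveness analysis sets each intervention against SS and leaves the three-way comparison secondary, so the headline result cannot show whether adding CM to MM is worth its cost

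*Protocol*

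**What the plan says.** Section 7.2.5 of the protocol states that the primary economic analysis will "compare costs and cost effectiveness at 12 month follow up of (a) SS compared to SS+MM, and (b) SS compared to SS+MM+CM". The next sentence adds: "Secondary analyses will explore SS compared to SS+MM compared to SS+MM+CM in a three-way comparison". Cost-effectiveness is to be assessed by ICERs, with acceptability curves for decision uncertainty. One threshold is cited: "Interventions with ICERs below £20,000 per additional QALY are generally considered cost-effective by NICE".

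The comparison with SS recurs elsewhere. The hypothesis in section 6 reads: "MM and MM+CM will be more cost-effective than SS alone at 12 months post-randomisation". Later in section 7.2.5, the purpose of the lifetime model is given as the long-term "cost-effectiveness of Medication Management (MM) and MM + Contingency Management (CM) compared to Standard Support".

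Section 7.1.1.3 describes how the arms relate. In the third arm, "participants will follow the same care pathway as those in the SS+MM arm of the trial but with the addition of CM". The added element is vouchers for completed MM sessions, "with a total value of up to £120 for completing all support sessions".

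**The concern.** A funder can adopt only one of SS, SS+MM and SS+MM+CM for a given patient, and the third contains the second. Whether CM is good value depends on what it adds to SS+MM in cost and QALYs. Neither primary comparison estimates that.

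When CM adds QALYs, the ICER of SS+MM+CM against SS is a QALY-weighted average of two steps: MM over SS, and CM over MM. A good-value first step can hide a poor-value second one. Both interventions could then look cost-effective in the headline result, while the vouchers cost more per QALY than the cited threshold or buy nothing. The lifetime model would carry the same framing into the long-term results.

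**Working it through.** **Inputs.** From the protocol: the £20,000 per QALY threshold (section 7.2.5), the £120 voucher ceiling (section 7.1.1.3) and allocation of 374/187/187 (section 7.2.2). The protocol states no expected cost, QALY gain or ICER, so there is no economic figure to reproduce. Assumed, relative to SS: SS+MM costs £200 more and gains 0.020 QALY. Assumed also: CM adds £120 to the cost of SS+MM, giving £320 in total.

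**Formulas.**
- ICER = difference in cost / difference in QALYs.
- Net benefit against SS = 20,000 × QALY gain − extra cost.

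**SS+MM against SS.** 200/0.020 = £10,000 per QALY. Net benefit = 400 − 200 = £200.

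**SS+MM+CM, by assumed total QALY gain over SS:**

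| Total gain | ICER v SS | ICER v SS+MM | Net benefit v SS |
|---|---|---|---|
| 0.019 | 320/0.019 = £16,842 | dominated (dearer, less effective) | 380 − 320 = £60 |
| 0.022 | 320/0.022 = £14,545 | 120/0.002 = £60,000 | 440 − 320 = £120 |
| 0.024 | 320/0.024 = £13,333 | 120/0.004 = £30,000 | 480 − 320 = £160 |
| 0.026 | 320/0.026 = £12,308 | 120/0.006 = £20,000 | 520 − 320 = £200 |
| 0.030 | 320/0.030 = £10,667 | 120/0.010 = £12,000 | 600 − 320 = £280 |

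Every row is below £20,000 against SS. In the first three rows SS+MM has the higher net benefit (£200), so SS+MM is the better choice. The fourth row is break-even; in the fifth the two comparisons agree.

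**The averaging, at 0.022.** (0.020/0.022) × 10,000 + (0.002/0.022) × 60,000 = 9,091 + 5,455, which is the £14,545 in the table apart from rounding.

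**Where the conflict lies.** SS+MM+CM passes against SS if its total gain exceeds 320/20,000 = 0.016. It fails against SS+MM if its total gain is below 0.020 + 120/20,000 = 0.026. The conflict therefore covers 0.016 to 0.026 QALY. CM has to add more than 120/20,000 = 0.006 QALY over SS+MM to clear the threshold.

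**Other assumptions.**
- *CM increment.* If CM adds £60, the limits are 260/20,000 = 0.013 and 0.020 + 0.003 = 0.023. At 0.022 the ICERs are 260/0.022 = £11,818 against SS and 60/0.002 = £30,000 against SS+MM.
- *Width of the range.* In general it is [gain of SS+MM + CM cost/20,000] − [(cost of SS+MM + CM cost)/20,000] = gain of SS+MM − cost of SS+MM/20,000. The CM cost cancels: it moves the range but does not change its width, which here is 0.020 − 0.010 = 0.010.
- *SS+MM cost and gain.* The range exists exactly when SS+MM is itself below £20,000 against SS. With CM at £120, an SS+MM cost of £100 and gain of 0.01 gives 0.011 to 0.016; £300 and 0.02 gives 0.021 to 0.026; £400 and 0.03 gives 0.026 to 0.036. At £200 and 0.01 (£20,000 exactly) or £300 and 0.01 (£30,000) there is none.

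**The case against.** The strongest reply is that the protocol already plans the comparison in question, in the sentence after the primary one and within the same evaluation. No test or gate would suppress it. A reader might infer that SS+MM+CM is never compared with SS+MM; the text does not support that, and what remains is a matter of ranking.

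A reader might also infer a decision rule that accepts any arm below £20,000 against SS. There is none. The threshold sentence describes what NICE generally considers cost-effective, and section 7.2.2 leaves final interpretation to the observed effects together with the economic outcomes. The plan would not wrongly accept CM by rule; its primary result could appear to support CM.

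Nor are the SS comparisons a mistake. They match objective III and the cost-effectiveness hypothesis in section 6, and they mirror the clinical contrasts. A three-way choice as the decision problem follows from the nested design and the stated interest in NHS adoption of CM, but it is not the protocol's declared primary question.

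The illustration shows that the conflict is possible, not that it is likely. Unearned vouchers would lower the £120; more attended sessions, administration and changes in other service use could move the increment either way. Details such as the form of the acceptability curve can be left to an analysis plan, and the lifetime outputs would allow an incremental ranking.

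All of this limits the point. It does not remove it, because the protocol itself fixes which comparison is primary, and that comparison cannot answer whether CM should be added to MM.

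**Conclusion.** The concern holds as a fault of hierarchy. For mutually exclusive nested strategies, the protocol makes the pairwise comparisons with SS primary, places the three-way comparison second, and frames the lifetime model against Standard Support only. The primary result can therefore show SS+MM+CM below £20,000 per QALY when its increment over SS+MM is above £20,000, or when it is dominated.

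The arithmetic is general; the size is illustrative. The range of 0.016 to 0.026 QALY rests on the assumed £200 and 0.020 QALY for SS+MM and on taking the voucher ceiling as the whole cost of CM. The problem does not arise if CM adds more than 0.006 QALY at that cost, or if SS+MM is not below the threshold against SS. The documents give no basis for saying which case will occur. The change is worth making because it costs little and alters what the headline economic result can conclude.

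**What to change.** In section 7.2.5, give the planned three-way comparison primary or co-primary status and define it as a full incremental analysis:
- order the three options by cost;
- remove dominated and extendedly dominated options;
- report each remaining ICER against the next non-dominated option;
- present acceptability curves with all three options together, or net benefit for each at £20,000.

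Keep the two comparisons with SS, because they answer the hypothesis in section 6. State that the lifetime model will be reported in the same incremental way.

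No extra data are needed. The price is some precision, since SS+MM+CM against SS+MM uses the two smaller arms. With 374/187/187 and equal variances, the ratio of its standard error to that of SS+MM against SS is √[(1/187 + 1/187)/(1/187 + 1/374)] = √(2/1.5) = 1.155, about 15% larger. The wider uncertainty should be shown with the result.
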